**5.2.1 Dose Modifications and Dosing Delays Tables for Specific Adverse Events for Pembrolizumab**

Subjects should receive appropriate supportive care measures as deemed necessary by the treating investigator, including but not limited to the items outlined below:

- Diarrhea: Subjects should be carefully monitored for signs and symptoms of enterocolitis (such as diarrhea, abdominal pain, blood or mucus in stool, with or without fever) and of bowel perforation (such as peritoneal signs and ileus). In symptomatic subjects, infectious etiologies should be ruled out, and if symptoms are persistent and/or severe, endoscopic evaluation should be considered.
  - In subjects with severe enterocolitis (Grade 3), pembrolizumab will be permanently discontinued, and treatment with systemic corticosteroids should be initiated at a dose of 1 to 2 mg/kg/day of prednisone or equivalent. When symptoms improve to Grade 1 or less, corticosteroid taper should be started and continued over at least 1 month.
  - In subjects with moderate enterocolitis (Grade 2), pembrolizumab should be withheld, and anti-diarrheal treatment should be started. If symptoms are persistent for more than one week, systemic corticosteroids should be initiated (e.g., 0.5 mg/kg/day of prednisone or equivalent). When symptoms improve to Grade 1 or less, corticosteroid taper should be started and continued over at

least 1 month. Regarding guidelines for continuing treatment with pembrolizumab, see Section 5.2.

- All subjects who experience diarrhea should be advised to drink liberal quantities of clear fluids. If sufficient oral fluid intake is not feasible, fluid and electrolytes should be substituted via IV infusion.
- Nausea/vomiting: Nausea and vomiting should be treated aggressively, and consideration should be given in subsequent cycles to the administration of prophylactic antiemetic therapy according to standard institutional practice. Subjects should be strongly encouraged to maintain liberal oral fluid intake.
- Anti-infectives: Subjects with a documented infectious complication should receive oral or IV antibiotics or other anti-infective agents as considered appropriate by the treating investigator for a given infectious condition, according to standard institutional practice.
- Immune-related adverse events: Please see Section 5.2.2 below and the separate guidance document in the administrative binder regarding diagnosis and management of adverse experiences of a potential immunologic etiology. Specific immune-related adverse events (irAEs) will be collected and designated as immune-related events of clinical interest (ECIs) as described in Section 5.2.2

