**Gastrointestinal Toxicity**

**Nausea/Vomiting/Dehydration:** In this protocol, the routine use of any and all anti-emetics is allowed as clinically appropriate; these include the use of dexamethasone and 5-HT3 receptor antagonists.

Patients should maintain adequate fluid and food intake because vorinostat's dose-limiting toxicities are anorexia, dehydration, diarrhea, and fatigue. In the setting of dysgeusia, popsicles and Gatorade have been found to be useful by some investigators to maintain adequate hydration. Patients should also be encouraged to seek a nutritional consult.

**Diarrhea:** Treat diarrhea promptly with appropriate supportive care, including loperamide. Instruct patients to begin taking loperamide at the first signs of 1) poorly formed or loose stool, 2) occurrence of more bowel movements than usual in one day, or 3) unusually high volume of stool. Loperamide should be taken in the following manner: 4 mg at first onset of diarrhea then 2 mg after each unformed stool. The daily dose should not exceed 16 mg. Loperamide should not be taken prophylactically. Advise patients to drink plenty of clear fluids to help prevent dehydration caused by diarrhea. Avoid loperamide if there is the presence of blood or mucus in the stool or if diarrhea is accompanied by fever. If diarrhea is suspected to be linked to pembrolizumab and is ≥ grade 3, hold dose until toxicity resolves to ≤ grade 1, then resume at dose given in prior cycle.

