### **5.2.2 Dose Modification and toxicity management for immune-related AEs associated with pembrolizumab**

AEs associated with pembrolizumab exposure, including coadministration with additional compounds, may represent an immunologic etiology. These immune-related AEs (irAEs) may occur shortly after the first dose or several months after the last dose of pembrolizumab/combination treatment and may affect more than one body system simultaneously. Therefore, early recognition and initiation of treatment are critical to reduce complications. Based on existing clinical study data, most irAEs were reversible and could be managed with interruptions of pembrolizumab//combination treatment, administration of corticosteroids and/or other supportive care. For suspected irAEs, ensure adequate evaluation to confirm etiology or exclude other causes. Additional procedures or tests such as bronchoscopy, endoscopy, skin biopsy may be included as part of the evaluation. Based on the severity of irAEs, withhold or permanently discontinue pembrolizumab and administer corticosteroids. Dose modification and toxicity management guidelines for irAEs associated with pembrolizumab/combination treatment are provided in Table 5.4.

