#### **Attribution of Toxicity:**

When study interventions are administered in combination, attribution of an adverse event to a single component is likely to be difficult. Therefore, while the investigator may attribute a toxicity event to the combination, to Vorinostat or Tamoxifen alone, or to pembrolizumab alone, for adverse events listed in Table 5.4, both interventions must be held according to the criteria in Table 5.4 Dose Modification and Toxicity Management Guidelines for Immune-Related Adverse Events Associated with Pembrolizumab.

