#### **Restarting Study Interventions:**

Participants may not have any dose modifications (no change in dose or schedule) of pembrolizumab in this study, as described in Table 5.4.

- If the toxicity does not resolve or the criteria for resuming treatment are not met, the participant must be discontinued from all study interventions.
- If the toxicities do resolve and conditions are aligned with what is defined in Table 5.4, the combination of Vorinostat, Tamoxifen and pembrolizumab may be restarted at the discretion of the investigator. In these cases where the toxicity is attributed to the combination or to Vorinostat or Tamoxifen alone, re-initiation of pembrolizumab as a monotherapy may be considered at the PI's discretion.

**Table 5.4 Dose modification and toxicity management guidelines for immune-related AEs associated with pembrolizumab monotherapy and IO Combinations**

irAEs	Toxicity Grade (CTCAE v5.0)	Action With Pembrolizumab	Corticosteroid and/or Other Therapies	Monitoring and Follow-up
Pneumonitis	Grade 2	Withhold	
 
• Administer corticosteroids (initial dose of 1 to 2 mg/kg prednisone or equivalent) followed by taper
 
• Add prophylactic antibiotics for opportunistic infections
 
	
 
• Monitor participants for signs and symptoms of pneumonitis
 
• Evaluate participants with suspected pneumonitis with radiographic imaging and initiate corticosteroid treatment
 

	Recurrent Grade 2, Grade 3 or 4	Permanently discontinue		
Diarrhea/Colitis	Grade 2 or 3	Withhold	
 
• Administer corticosteroids (initial dose of 1 to 2 mg/kg prednisone or equivalent) followed by taper
 
	
 
• Monitor participants for signs and symptoms of enterocolitis (ie, diarrhea, abdominal pain, blood or mucus in stool with or without fever) and of bowel perforation (ie, peritoneal signs and ileus)
 
• Participants with ≥Grade 2 diarrhea suspecting colitis should consider GI consultation and performing endoscopy to rule out colitis
 
• Participants with diarrhea/colitis should be advised to drink liberal quantities of clear fluids. If sufficient oral fluid intake is not feasible, fluid and electrolytes should be
 

	Recurrent Grade 3 or Grade 4	Permanently discontinue		

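### The pembrolizumab rules for grade 3 and grade 4 diarrhea/colitis conflict across Sections 5.2, 5.2.1, 6.5.2 and Table 5.4, and nothing says which prevails

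*Combined protocol and SAP*

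**What the plan says.** Four places tell the investigator what to do with pembrolizumab when diarrhea or colitis occurs.

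- **Section 5.2, Gastrointestinal Toxicity.** The rule for diarrhea reads: "linked to pembrolizumab and is ≥ grade 3, hold dose until toxicity resolves to ≤ grade 1, then resume at dose given"; the dose meant is that of the preceding cycle. There is no upper grade and no limit on recurrence.
- **Section 5.2.1, Diarrhea bullet.** "In subjects with severe enterocolitis (Grade 3), pembrolizumab will be permanently discontinued". First and recurrent events are not distinguished, and grade 4 is not mentioned. For grade 2, pembrolizumab is withheld and "If symptoms are persistent for more than one week, systemic corticosteroids should be initiated (e.g., 0.5 mg/kg/day of prednisone or equivalent"). At both grades the steroid taper starts once symptoms reach grade 1 or less and lasts at least 1 month.
- **Section 6.5.2.** The same enterocolitis bullets again.
- **Section 5.2.2, Table 5.4, Diarrhea/Colitis row.** Withhold for grade 2 or 3; discontinue permanently for "Recurrent Grade 3 or Grade 4". The steroid instruction is "Administer corticosteroids (initial dose of 1 to 2 mg/kg prednisone or equivalent) followed by taper", with no waiting period.

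Section 5.2.2 states that "guidelines for irAEs associated with pembrolizumab/combination treatment are provided in Table 5.4" and that, for events listed there, "both interventions must be held according to the criteria in Table 5.4". For immune-related events, Section 5.2.1 refers the reader to Section 5.2.2 and to "the separate guidance document in the administrative binder regarding diagnosis and management of adverse experiences".

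**The concern.** These are instructions for the same clinical event, and they lead to different actions. An investigator facing a first grade 3 colitis can stop pembrolizumab for good under 5.2.1 or withhold it under Table 5.4, and either action follows the protocol. At grade 4 the stakes are higher: Table 5.4 forbids further pembrolizumab, while the Section 5.2 sentence, as worded, lets treatment resume once the event has settled to grade 1 or less.

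What is at stake is patient safety, like treatment of like patients, and the ability to audit adherence. A monitor cannot classify a discontinuation or a restart as a deviation when the protocol supports both.

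**Working it through.** No arithmetic applies. The check sets the instructions side by side by grade and then looks for text that would reconcile them.

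| Event | 5.2 Gastrointestinal Toxicity | 5.2.1 and 6.5.2 | Table 5.4 |
|---|---|---|---|
| Grade 2 | no pembrolizumab rule (starts at grade 3) | withhold; steroid after more than one week, e.g. 0.5 mg/kg/day | withhold; steroid 1 to 2 mg/kg, no wait |
| First grade 3 | hold, then resume | discontinue permanently | withhold |
| Recurrent grade 3 | hold, then resume | discontinue permanently | discontinue permanently |
| Grade 4 | hold, then resume | not named | discontinue permanently |

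**Are these the same event?** Yes. In 5.2.1 and 6.5.2 the enterocolitis rules sit under the Diarrhea bullet, and the Diarrhea/Colitis row of Table 5.4 asks for monitoring for enterocolitis.

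**Which drug does the Section 5.2 sentence hold?** It does not say. Its condition is diarrhea linked to pembrolizumab, and the opening of Section 5.2 says the agent responsible is the one to modify, so pembrolizumab is the natural reading. It remains an inference.

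**Does any text set precedence?**

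1. Sections 5.2.1 (immune-related bullet) and 5.2.2 direct immune-related events to Table 5.4. Neither cancels the mandatory discontinuation in 5.2.1 and 6.5.2 or the resumption in 5.2.
2. The cross-references do not settle it. On continuing pembrolizumab, 6.5.2 sends the reader to 5.2.1, and 5.2.1 sends the reader to Section 5.2, which contains both the hold-and-resume sentence and Table 5.4.
3. The instruction in Section 5.2 to use the most stringent modification applies when several conditions occur together, and is introduced for febrile neutropenia and blood counts. It does not rank competing instructions for one event.
4. The grade 4 stop under Other Non-hematological Toxicities is in a table headed for vorinostat.
5. Section 3.1 says pembrolizumab is modified according to the manufacturer's guidelines, without identifying which text that means.
6. Section 3.5 says a patient whose severe or life-threatening event recurs at the same or a higher grade on re-challenge should come off trial treatment. That agrees with Table 5.4 on recurrent grade 3. But it presupposes that re-challenge after a life-threatening event can happen, so it does not resolve grade 4.

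**What would be lost if Table 5.4 simply replaced the rest?** The table gives no resumption grade for diarrhea/colitis; its footnote allowing resumption at grade 2 or less is attached only to endocrine rows. The grade 1 threshold appears only in Section 5.2. The table also says only that steroids are tapered; the starting point and minimum duration of the taper for diarrhea/colitis are in 5.2.1 and 6.5.2.

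**The case against.** The best defense is that Table 5.4 already governs. Section 5.2.2 requires interventions to be held by its criteria whatever the attribution, and 5.2.1 itself points there for immune-related events. This carries weight: Table 5.4 is probably what was intended. It does not remove the conflict, because the competing sentences are still in force and two of them use mandatory wording.

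A second objection is that the Section 5.2 sentence belongs to vorinostat: it sits among vorinostat rules, uses phrasing found in the vorinostat tables, and names no drug to hold. That is why the grade 4 and recurrent grade 3 items are stated as the natural reading rather than as certain. The first grade 3 conflict between 5.2.1/6.5.2 and Table 5.4 does not depend on it.

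A third objection concerns grade 2. The 5.2.1 and 6.5.2 bullets are introduced as supportive care at the investigator's judgment, and the 0.5 mg/kg/day dose is an example. The steroid difference is therefore minor.

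A reader might go further and infer that the pembrolizumab dose and schedule rules contradict each other generally, because 5.2.2 bars changes in dose or schedule while 8.2 allows an arm-level reduction to 75%. The documents do not establish that. The bar appears under the heading on restarting treatment and cites Table 5.4, so it can be read alongside 8.2, and Section 5.1 expressly allows longer cycle intervals for toxicity. That is no part of this point.

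**Conclusion.** The conflict is real and should be fixed. For a first grade 3 diarrhea/colitis the protocol gives three instructions: discontinue, withhold, or hold and resume. For grade 4 and recurrent grade 3 it gives two: discontinue permanently, or hold and resume at the prior dose, if the Section 5.2 sentence refers to pembrolizumab.

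The rule reaches every patient, since both arms receive pembrolizumab; Section 8.1.1 gives enrollment as 24 to 65, most likely 46. How often it will be needed cannot be estimated usefully from the documents. The pilot in Section 1.3.1.2 reports grade 2 colitis in 3% and lists no grade 3 or 4 colitis.

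A reader might infer that the trial's statistical design is compromised. It is not: no stated sample size, power or alpha changes. Who stays on pembrolizumab could differ with the section followed, but the documents give no basis for putting a size on any effect on the 24-week endpoint. Nor do they show that the sponsor intends re-treatment after grade 4. The wording permits it on its natural reading, and Table 5.4 points the other way.

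The separate guidance document in the administrative binder was not available for this review, so its content is not assumed either way.

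**What to change.** State one pembrolizumab rule for diarrhea/colitis and use it in Section 5.2 (Gastrointestinal Toxicity), 5.2.1, 6.5.2 and Table 5.4.

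1. **Grade 4 and recurrent grade 3:** permanently discontinue. Limit the Section 5.2 sentence so that it no longer allows resumption after either, and have it name pembrolizumab.
2. **First grade 3:** the sponsor confirms one action, either withholding as in Table 5.4 (the likely intent) or the stricter permanent discontinuation of 5.2.1 and 6.5.2. This is a clinical decision that the documents do not settle. Align all four places to it.
3. **Keep what Table 5.4 lacks:** add to its Diarrhea/Colitis row the resumption threshold of grade 1 or less from Section 5.2, and the taper rule (start at grade 1 or less, continue at least 1 month) from 5.2.1 and 6.5.2. The threshold is now written only for grade 3 and above, so the sponsor should confirm that it also applies after a grade 2 hold.
4. **Minor, in the same edit:** align the grade 2 steroid start and dose, and check that the binder guidance agrees.

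The cost is a wording amendment in four places, with the approvals Section 9.4 requires, plus one clinical decision by the sponsor. Sample size, power, alpha and data collection do not change.

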## 6.5.2 Rescue Medications & Supportive Care

### Supportive Care Guidelines

Subjects should receive appropriate supportive care measures as deemed necessary by the treating investigator, including but not limited to the items outlined below:

- Diarrhea: Subjects should be carefully monitored for signs and symptoms of enterocolitis (such as diarrhea, abdominal pain, blood or mucus in stool, with or without fever) and bowel perforation (such as peritoneal signs and ileus). In symptomatic subjects, infectious etiologies should be ruled out, and if symptoms are persistent and/or severe, endoscopic evaluation should be considered.
  - In subjects with severe enterocolitis (Grade 3), pembrolizumab will be permanently discontinued, and treatment with systemic corticosteroids should be initiated at a dose of 1 to 2 mg/kg/day of prednisone or equivalent. When symptoms improve to Grade 1 or less, corticosteroid taper should be started and continued over at least 1 month.
  - In subjects with moderate enterocolitis (Grade 2), pembrolizumab should be withheld, and anti-diarrheal treatment should be started. If symptoms are persistent for more than one week, systemic corticosteroids should be initiated (e.g., 0.5 mg/kg/day of prednisone or equivalent). When symptoms improve to Grade 1 or less, corticosteroid taper should be started and continued over at least 1 month. Regarding guidelines for continuing treatment with pembrolizumab, see Section 5.2.1.
  - All subjects who experience diarrhea should be advised to drink liberal quantities of clear fluids. If sufficient oral fluid intake is not feasible, fluid and electrolytes should be substituted via IV infusion.
- Nausea/vomiting: Nausea and vomiting should be treated aggressively, and consideration should be given in subsequent cycles to the administration of prophylactic antiemetic therapy according to standard institutional practice. Subjects should be strongly encouraged to maintain liberal oral fluid intake.
- Anti-infectives: Subjects with a documented infectious complication should receive oral or IV antibiotics or other anti-infective agents as considered appropriate by the treating investigator for a given infectious condition, according to standard institutional practice.
- Immune-related adverse events: Please see Section 5.2 below and the separate guidance document in the administrative binder regarding diagnosis and management of adverse experiences of a potential immunologic etiology.

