## **6.6 Prohibited Medications**

Subjects are prohibited from receiving the following therapies during the Screening and Treatment Phase (including retreatment for post-complete response relapse) of this trial:

- Anti-cancer systemic chemotherapy or biological therapy
- Immunotherapy not specified in this protocol
- Chemotherapy not specified in this protocol
- Investigational agents other than Pembrolizumab
- Radiation therapy

- Note: Radiation therapy to a symptomatic solitary lesion or the brain may be allowed after consultation with the study PI and Merck.
- Live vaccines within 30 days prior to the first dose of trial treatment and while participating in the trial. Examples of live vaccines include, but are not limited to, the following: measles, mumps, rubella, chicken pox, yellow fever, rabies, BCG, and typhoid (oral) vaccine. Seasonal influenza vaccines for injection are generally killed virus vaccines and are allowed; however, intranasal influenza vaccines (e.g., Flu-Mist®) are live attenuated vaccines and are not allowed.
- Glucocorticoids for any purpose other than to modulate symptoms from an event of clinical interest of suspected immunologic etiology. The use of physiologic doses of corticosteroids may be approved after consultation with the study PI and Merck.

Subjects who, in the assessment by the investigator, require the use of any of the aforementioned treatments for clinical management should be removed from the trial. Subjects may receive other medications that the investigator deems to be medically necessary.

The Exclusion Criteria describes other medications, which are prohibited in this trial.

There are no prohibited therapies during the Post-Treatment Follow-up Phase.

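### First Grade 3 colitis: sections 5.2.1 and 6.5.2 stop pembrolizumab permanently, Table 5.4 only withholds it, and the text favouring the table does not say it overrides them

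*Combined protocol and SAP*

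**What the plan says.** **Sections 5.2.1 and 6.5.2 (diarrhea item, same rules in both).** At Grade 3: "In subjects with severe enterocolitis (Grade 3), pembrolizumab will be permanently discontinued", with systemic steroids at 1 to 2 mg/kg/day. At Grade 2, pembrolizumab is withheld, antidiarrheal treatment starts, and then: "If symptoms are persistent for more than one week, systemic corticosteroids should be initiated (e.g., 0.5 mg/kg/day of prednisone or equivalent". On continuing pembrolizumab, 5.2.1 refers the reader to Section 5.2 as a whole, while 6.5.2 says "Regarding guidelines for continuing treatment with pembrolizumab, see Section 5.2.1".

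**Table 5.4 (in 5.2.2), Diarrhea/Colitis row.** Grades 2 and 3 share one action, withhold. Permanent discontinuation is reserved for "Recurrent Grade 3 or Grade 4". The steroid entry reads "Administer corticosteroids (initial dose of 1 to 2 mg/kg prednisone or equivalent) followed by taper".

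**Section 5.2, Gastrointestinal Toxicity, diarrhea paragraph.** The instruction reads, in part: "diarrhea is suspected to be linked to pembrolizumab and is ≥ grade 3, hold dose until toxicity resolves to ≤ grade 1, then resume". The restart uses the prior cycle's dose. The sentence does not name the drug to be held.

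**Linking text.** The immune-related item in 5.2.1 points to 5.2.2 and to a guidance document in the administrative binder, which is not part of the file. In 5.2.2, the Attribution of Toxicity paragraph makes holds for events listed in Table 5.4 follow that table's criteria, whichever drug is blamed. The Restarting paragraph ties resumption to the table's conditions. Section 5.2.2 also says: "For suspected irAEs, ensure adequate evaluation to confirm etiology or exclude other causes".

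**The concern.** Permanent discontinuation and withholding cannot both be carried out for one event. Two clinicians acting in good faith could treat the same first Grade 3 colitis differently: one ends pembrolizumab for that patient, the other holds it and may re-challenge. A third reader, relying on the diarrhea paragraph of 5.2, could resume even after Grade 4, where Table 5.4 stops the drug.

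At Grade 2 the issue is softer. Both rules withhold pembrolizumab, so only the steroid step differs. One reader waits more than a week; another gives steroids once an immune cause is suspected and worked up.

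Both arms receive pembrolizumab, so both are exposed to the inconsistency. What is at stake is patient management and uniform conduct.

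**Working it through.** **Side-by-side comparison**

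| Event | 5.2.1 and 6.5.2 | Table 5.4 | 5.2, diarrhea paragraph |
|---|---|---|---|
| First Grade 3, pembrolizumab | Stop permanently | Withhold; restart possible | Hold to Grade 1 or less, then resume (drug not named) |
| Recurrent Grade 3, pembrolizumab | Already stopped at the first | Stop permanently | Hold and resume, as worded |
| Grade 4, pembrolizumab | Grade 4 not mentioned | Stop permanently | Hold and resume, as worded |
| Grade 2, pembrolizumab | Withhold | Withhold | Not covered |
| Grade 2, steroids | After more than 1 week; 0.5 mg/kg/day as an example | Initial 1 to 2 mg/kg; no waiting condition, no start time | Not covered |

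The first row is a direct contradiction between two definite instructions. The Grade 4 row is a contradiction if the 5.2 sentence refers to pembrolizumab. The last row sets a stated wait against silence on timing, so it is an ambiguity.

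**Are these the same events?** The monitoring column of the Table 5.4 row covers enterocolitis and bowel perforation, with the same signs as 5.2.1. Section 6.6 adds some support, because it prohibits "Glucocorticoids for any purpose other than to modulate symptoms from an event of clinical interest of suspected immunologic etiology"; on that reading the steroid steps in 5.2.1 already concern suspected immune events. That support is limited. Section 5.2 allows dexamethasone as an antiemetic and Table 5.5 lists corticosteroids for infusion reactions. The enumerated events of clinical interest are only overdose and liver-test elevations, although 5.2.1 separately designates immune-related events as such.

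**Does any text decide between them?**
- Attribution and Restarting paragraphs (5.2.2): they favour Table 5.4 for holding and restarting in combination treatment. They do not mention 5.2.1, 6.5.2 or steroid timing.
- Cross-references: 5.2.1 points to the whole of 5.2, which contains all three rules. 6.5.2 points back to 5.2.1.
- Most-stringent rule at the start of 5.2: it concerns febrile neutropenia and blood counts. Stretched to colitis, it would favour 5.2.1 at first Grade 3, the opposite of the Attribution paragraph.

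**How many patients?** The plan gives no projection. Inputs: Grade 2 colitis in 3% of 34 pilot patients (1.3.1.2), that is 0.03 × 34 ≈ 1 case; six of the 34 never received pembrolizumab, leaving 34 − 6 = 28; planned enrollment 65, likely enrollment 46 (8.1.1). Ranges are exact (Clopper-Pearson) 95% intervals.

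| Grade 2 colitis | 1/34 | 1/28 (assumes the case received pembrolizumab) |
|---|---|---|
| Rate | 2.94% (0.074% to 15.33%) | 3.57% (0.090% to 18.35%) |
| Expected in 65 | 65/34 = 1.91 (0.05 to 9.96) | 65/28 = 2.32 (0.06 to 11.93) |
| Expected in 46 | 46/34 = 1.35 (0.03 to 7.05) | 46/28 = 1.64 (0.04 to 8.44) |
| Chance of at least one in 65 | 1 − (33/34)^65 = 0.856 (0.047 to >0.999) | 1 − (27/28)^65 = 0.906 (0.057 to >0.999) |

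For Grade 3, colitis is absent from the pilot's grade 3-4 list. If that list is complete, zero events in 28 gives an upper limit of 1 − 0.025^(1/28) = 12.3%, and 0.123 × 65 ≈ 8.0 patients. With 34 as the denominator the limit is 10.3%, and 0.103 × 65 ≈ 6.7.

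**The case against.** The best counter-argument is that Table 5.4 already governs. Section 5.2.2 presents it as the guideline for immune-related events. The Attribution paragraph is phrased as a requirement, and restarting is tied to the table. The lists in 5.2.1 and 6.5.2 open as supportive care to be used as the investigator sees fit, and both send immune-related events elsewhere. This stands in part: someone might infer that the protocol says nothing about which rule applies, and that would be wrong. It does not resolve the conflict, because 5.2.1 is headed as dose modification, its Grade 3 instruction is equally mandatory, and nothing says the table displaces it.

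Second, the Grade 2 difference could be read as a firm contradiction in steroid timing and dose. The documents do not support that. The table gives no start time, 5.2.2 calls for evaluation first, the row advises considering GI consultation and endoscopy, and 0.5 mg/kg is only an example.

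Third, the hold-and-resume sentence in 5.2 may be meant for vorinostat. Resuming at the prior cycle's dose resembles the vorinostat tables, and 5.2.2 allows no pembrolizumab dose change. This stands as a reason to edit that sentence narrowly.

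Fourth, the binder guidance may settle matters in practice. That cannot be checked here, and the protocol text should agree with itself regardless.

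**Conclusion.** The contradiction at first Grade 3 is real and in current text. It depends on none of the dose or timing caveats. The 5.2 sentence adds a conflict at Grade 4 if it applies to pembrolizumab. The Grade 2 steroid difference is secondary, an ambiguity worth clearing in the same edit.

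The numbers affected are probably small and very uncertain: about 2 Grade 2 cases in 65, and for Grade 3 only an upper limit of about 8 in 65. These figures rest on one pilot event, on the pilot's toxicity list being complete, and on pilot rates carrying over. Every pilot patient was assigned vorinostat, so the Arm B rate is unknown. The projection counts colitis only, while the rules also cover diarrhea.

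Two further inferences should be resisted. The documents do not show that the one-week steroid wait causes harm; pembrolizumab is withheld meanwhile under either rule. Nor do they show an effect on the response analysis, the error rates or the arm comparison. The point is a safety and conduct correction that should be made.

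**What to change.** 1. In 5.2.1 and 6.5.2, replace the Grade 2 and Grade 3 text on pembrolizumab action and steroid start with: *For suspected immune-related diarrhea/colitis, Table 5.4 governs in both arms.* The basis is the introduction to 5.2.2 and its Attribution and Restarting paragraphs.
2. Keep the infection work-up, endoscopy, fluids and the taper of at least 1 month, since Table 5.4 gives no taper length.
3. In the diarrhea paragraph of 5.2, add: *For pembrolizumab, follow Table 5.4; do not resume after Grade 4 or recurrent Grade 3.* Leave any vorinostat hold in place.
4. Check the wording against the binder guidance before submission.
5. If the sponsor prefers permanent discontinuation at first Grade 3, amend Table 5.4 instead, and align the 5.2 sentence, so that only one rule remains.

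The cost is wording in three places plus a protocol amendment, which 9.4 sends to the PRC and IRB. With Table 5.4 governing, some self-limiting Grade 2 cases may receive steroids earlier, and some patients may be re-challenged after a first Grade 3 event.
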